# 9.7.2 Advancing the understanding of the patient population prescribed rivaroxaban in combination with standard oral antiplatelet therapy for ACS in the secondary care hospital setting including drug utilisation characteristics

The following relates to Section 8.2 secondary objective 1.

<sup>1 e.g. when the shape parameter (p) for the Weibull model is equal to one, the hazard is estimated to be constant over time, if p is greater than one the hazard is increasing, if p is less than one the hazard is decreasing. The hazard function will be determined as non-constant if the 95% CI excludes the value one

#### 9.7.2.1 Descriptive exploratory analysis

Valid cohort demography (patient self-reported: age, gender, ethnicity, socioeconomic index) will be presented separately for both rivaroxaban and the contextual cohort, as reported at index date using all available information from questionnaires (completed by patient and specialist HCP). Other patient self-reported general health factors [BMI, weight, height, smoking and alcohol use] and indication-related characteristics [primary (and secondary if provided) diagnosis/decision, date and duration since first ever recorded; reported bleeding risk factors]; antiplatelet treatment initiation programme by specialist HCP (index date, dose and frequency) and prescribing reasons. A synopsis of pre-index and concurrent relevant morbidities and medication use will also be provided.

For rivaroxaban cohort only, patient subgroups of special interest (Table 5 – 'off-label' use defined as arising from contraindications and those for which: a) precautions for use are recommended; b) appropriate clinical monitoring is recommended; c) limited information is available; and d) selected concomitant drug use) will be summarised in order to inform on real-life use of rivaroxaban. The proportion of patients within each special population sub-group prescribed rivaroxaban who had *one or more* relevant characteristics/conditions/co-prescribed medications at index date will also be summarised within each indicator group by simple aggregation of counts (Table 5).

Further stratification within-cohort by calendar period *may* also be undertaken to identify any cohort effects or trends that may be emerging.

#### Table 5. Special Population Indicators of Use for Rivaroxaban

5a) Indicators of Contraindicated Use (Patients can have up to 5 indicators)

Treatment for medical indications other than licensed indications

Clinically significant active bleeding

Hepatic disease associated with coagulopathy and clinically relevant bleeding risk

Use in pregnancy and lactation

Hypersensitivity to the active substance or to any of the excipients

5b) Indicators of Use with Special Warnings or Precautions (*Patients can have up to 11 indicators*)

Patients with liver cirrhosis with moderate hepatic impairment (classified as Child Pugh B), not associated with coagulopathy

Severe renal impairment (patients with creatinine clearance < 30 ml/min)

Moderate renal impairment (patients with creatinine clearance 30-49 ml/min)

Congenital or acquired bleeding disorders

Uncontrolled severe arterial hypertension

Active ulcerative gastrointestinal disease

Recent gastrointestinal ulcerations

Vascular retinopathy

Recent intracranial or intracerebral haemorrhage

Intraspinal or intracerebral vascular abnormalities

Recent brain, spinal or ophthalmological surgery.

5c). Indicators of Use in Patients with Limited Information *(Patients can have up to 1 indicator)* 

Children aged  $\leq$  15 years

5d) Indicators of Use with Potential Drug-Drug Interactions *(Patients can have up to 4 indicators)* 

Concomitant systemic treatment with azole-antimycotics, e.g ketoconazole or HIV protease inhibitors

Concomitant treatment with CYP3A4 inhibitors/inducers or P-gp inhibitors

Concomitant treatment with other anticoagulants

Concomitant use with NSAIDs and platelet aggregation inhibitors

#### 9.7.2.2 Understanding treatment decisions between trusts

A multilevel framework approach with its simultaneous examination of characteristics of individuals at one level and the setting in which they are located at another level offers a contextual framework for understanding the way in which setting can affect patient health. Clustering can also arise from sampling strategy; this SCEM study involves HCPs within hospital settings as well as individual patients which generates a hierarchical clustered structure. Individual patients treated by the same HCP within a hospital can be expected to be more similar than if sampling were truly random. Because of hierarchical structure of the data, with patients (first level) nested within HCP specialist clinics (second level) which are in turn nested within trusts (third level) the probability of prescribing rivaroxaban will be analysed using multilevel logistic regression analysis of pooled study data. This type of analysis reveals the role of different levels for understanding drug prescription and utilisation. Thus it will enable the study of a) the influence of the patient, HCP and trust characteristics on anticoagulation use simultaneously and b) the variance in prescribing.

The multivariate analysis will inform on the influence of those characteristics identified for each level as significant from a univariate analysis of association between those characteristics and treatment (rivaroxaban or not). A base model will describe the crude association between treatment decision, HCP and trust. This will give the variance estimate for levels 2 and 3 without correcting for differences that might exists in patients within each cluster. In the first model, the variance estimates for levels 2 and 3 will be obtained, accounting for significant predictors (identified from univariate analysis). This will inform on which patient characteristics are associated with treatment with rivaroxaban. The association between selected fixed level 1 patient characteristics and prescribing anticoagulation medication will be expressed using odds ratios and 95% confidence intervals from the regression coefficients and their standard error (SE) in the fixed-effect part of the multi-level analysis. In the random-effects part of the multi-level analysis, the variance (SE) at HCP and trust level will be obtained as will the variance that is unexplained by these patient characteristics. A second model will allow level 2 HCP factors to be explored, whilst a third model will allow level 3 (trust) factors to be explored. Thus this analysis will identify source of variation in prescribing and identify whether there are significant differences in treatment decisions between trusts after taking into account individual differences.

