2.1.4 Which formal hypothesis(-es) is (are) to be tested?				
2.1.5 If applicable, that there is no a priori hypothesis?				

Comments:

There are no formal hypotheses to be tested in this study

			Page Number(s)
3.1 Is the study design described? (e.g. cohort, case-control, randomised controlled trial, new or alternative design)	$\boxtimes$		18
3.2 Does the protocol specify the primary and secondary (if applicable) endpoint(s) to be investigated?			28
3.3 Does the protocol describe the measure(s) of effect? (e.g. relative risk, odds ratio, deaths per 1000 person-years, absolute risk, excess risk, incidence rate ratio, hazard ratio, number needed to harm (NNH) per year)			31

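### Section 9.7.2.2 lets only univariately significant characteristics into the multilevel prescribing model, so its trust comparison does not adjust for case-mix factors that miss the screen

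*Protocol*

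**What the plan says.** Section 9.7.2.2 plans a three-level logistic regression (patients within HCP clinics within trusts) of whether rivaroxaban was prescribed. The reason given is clustering: "Individual patients treated by the same HCP within a hospital can be expected to be more similar than if sampling were truly random".

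Covariates enter by a significance screen applied at every level: "The multivariate analysis will inform on the influence of those characteristics identified for each level as significant from a univariate analysis of association". The first model then obtains the HCP and trust variances after adjusting for the predictors that passed. Of that model the section says: "This will inform on which patient characteristics are associated with treatment with rivaroxaban". Its odds ratios are given with 95% confidence intervals. On the higher levels it says: "A second model will allow level 2 HCP factors to be explored, whilst a third model will allow level 3 (trust) factors to be explored". The final product is that the analysis will "identify whether there are significant differences in treatment decisions between trusts after taking into account individual differences".

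The section gives no significance level for the screen, names no characteristic to be retained regardless of it, and does not say whether the univariate tests carry the HCP and trust random effects. The analysis serves secondary objective 1 (sections 8.2 and 9.7.2). The checklist in Annex 2 states: "There are no formal hypotheses to be tested in this study".

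**The concern.** The method does not fully deliver the stated conclusion. A comparison of trusts that allows for individual differences needs the relevant patient factors in the model. Here a factor is allowed for only if it passes a marginal test. A real case-mix factor that is uncommon, weak, or hidden marginally by an opposite gradient between trusts can fail, and what it contributes then stays in the HCP and trust variances. A multilevel model exists to separate within-trust from between-trust effects; a one-at-a-time gate in front of it works against that.

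The same data also select and estimate. Factors near the threshold are retained when their estimate happens to be large, so retained odds ratios lie too far from 1 on average, and the intervals are computed as if nothing had been selected.

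At stake are the two products of this analysis: the account of which patients receive rivaroxaban, and the statement about variation between trusts. The rule is fixed in the protocol. A statistical analysis plan could set the threshold, but could not remove the screen without departing from the protocol.

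**Working it through.** **The plan's own figure.** Section 9.5 gives 1193 per cohort for an incidence of 0.5% within ±0.4%. n = 1.96² × 0.005 × 0.995 / 0.004² = 1194.5; with a finite-population correction at an assumed population of 1,000,000 it is 1193.03. The figure reproduces. It was chosen for the bleeding incidence; the prescribing model has no stated threshold, number of candidates, number of trusts or power.

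**Inputs.** From the protocol: 1193 per cohort, 1:1 (sections 9.2.2 and 9.5). Assumed, because the protocol gives none: the screening threshold, factor prevalences, odds ratios and trust variance. Clustering is ignored in steps 1 and 2.

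**Step 1: chance that a real binary patient factor passes.** With prevalence q in the comparator cohort and odds ratio OR, the rivaroxaban prevalence p₁ follows from odds q/(1−q) × OR. Then μ = (p₁ − q) / √[(p₁(1−p₁) + q(1−q))/1193], and the chance of passing a two-sided 5% test is Φ(μ − 1.96).

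- q = 10%, OR 1.3: p₁ = 0.1262, μ = 0.0262/0.01296 = 2.02, chance 53%.
- q = 5%, OR 1.3: p₁ = 0.0640, μ = 0.0140/0.00949 = 1.48, chance 32%.
- q = 30%: OR 1.2 gives 55%, OR 1.3 gives 85%, OR 1.5 gives 99.7%.

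With a looser 20% threshold (1.28 in place of 1.96), the first two become Φ(0.74) = 77% and Φ(0.20) = 58%. Common, strong factors get in; weaker or rarer ones often do not.

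**Step 2: what selection does to the retained odds ratio.** If the joint estimate is close to the univariate one, the mean test statistic given passing is μ + φ(a)/[1 − Φ(a)], with a = 1.96 − μ.

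- q = 10%: 2.02 + 0.398/0.525 = 2.78. The log odds ratio is inflated by 2.78/2.02 = 1.375, so a true 1.3 averages exp(0.262 × 1.375) = 1.43.
- q = 5%: 1.48 + 0.355/0.315 = 2.61, factor 1.76, average exp(0.262 × 1.76) = 1.59.
- At a 20% threshold the averages are about 1.37 and 1.47.

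Coverage given passing is [0.975 − Φ(a)] / [1 − Φ(a)]. For q = 10% this is (0.975 − 0.475)/0.525 = 95%; for q = 5%, (0.975 − 0.685)/0.315 = 92%. For real factors of this size the damage is to the point estimate more than to coverage. A null factor that passes a 5% screen is different: its univariate 95% interval excludes 1 by construction.

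**Step 3: trust variance left by weak omitted factors.** Approximate it by K × (ln OR)² × s², with K omitted factors and s the between-trust SD of prevalence. At the top of the range tried (K = 8, OR 1.3, s = 0.10): 8 × 0.0688 × 0.01 = 0.0055. At the bottom (K = 3, OR 1.2, s = 0.05): 0.0003. Against an assumed trust variance of 0.25 the top value is 0.0055/0.25 = 2.2%.

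**Step 4: a masked factor.** In one deliberately adverse simulation (100 trusts of 24 patients, within-trust OR 2, trust prevalences with SD 0.2, trust intercepts falling by 4 per unit of prevalence, other trust variance 0.25), the factor passed a single-level 5% screen in 23% of runs. Roughly, ignoring truncation of the prevalences, the trust variance with the factor in the model is 0.25 + 4² × 0.04 = 0.89. Without it, it is 0.25 + (4 − 0.69)² × 0.04 = 0.69. So a masked factor can matter, and its omission can lower the trust variance as well as raise it.

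**The case against.** The case for leaving the section alone is reasonable. This is a drug-utilisation objective, the checklist disclaims formal hypotheses, HCP and trust factors are described as explored, and no bleeding result depends on the model. Passing the screen is only an entry gate, since selected factors are re-estimated jointly with intervals. At 1193 per cohort, strong common factors pass almost always, and those that fail carry little trust variance unless masked. All of this stands, and it limits the size of the point. It does not remove it: the section still promises a trust comparison net of individual differences, and still makes the screen the only route to adjustment.

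Two stronger readings are tempting and are not supported.

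- **That chance predictors will be claimed at a full 5% level.** With independent null candidates, 1 − 0.95^k gives 40%, 64% and 79% for k = 10, 20 and 30. But the protocol states neither a threshold nor a number of candidates, the figures assume every candidate is null although section 9.9 expects channelling by patient characteristics, and entry to a jointly fitted model is not yet a claim.
- **That the screen ignores clustering and so over-selects trust-level characteristics.** This holds only if the univariate tests are single-level, which the protocol does not say; a one-covariate multilevel model is an equally open reading. Any rate also needs a number of trusts and a variance that the protocol does not give.

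Nor can case-mix adjustment draw freely on the 12-week questionnaire: section 9.3.2 shows it also records treatment changes and events after the prescribing decision.

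**Conclusion.** The point holds as a modest flaw in a stated method. Univariate significance is the only way into the model behind the adjusted trust comparison, so factors that miss the screen are not taken into account, and odds ratios of factors near the threshold are reported too far from 1 with intervals that ignore the selection.

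Under a 5% threshold and 1193 per cohort, real factors with OR 1.3 and prevalence 5% to 10% are lost in about half to two thirds of studies (47% to 68%). The trust variance attributable to weak omitted factors is small, at most about 2% of an assumed 0.25; a masked factor could shift it more, in either direction. These sizes rest on the assumed threshold, prevalences, odds ratios and variances. The consequence is confined to secondary objective 1.

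**What to change.** In section 9.7.2.2, delete the univariate screen as an entry rule and state instead:

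- Model 1 contains a pre-specified list of patient characteristics known at or before the prescribing decision: age, sex, ACS type, baseline bleeding risk factors, prior antithrombotic use, relevant medical history and renal function at index. They are entered together whatever their univariate result. Very rare items are combined or omitted for sparseness. Items from the 12-week questionnaire are used only where they describe the patient's state at or before index.
- Models 2 and 3 add pre-specified HCP and institution characteristics.
- Univariate associations are tabulated for description only, from models with the same random effects.
- Odds ratios are interpreted as exploratory.

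No new data are needed. The cost is a somewhat larger model and slightly wider intervals. With 1193 patients in each treatment group, 20 to 30 parameters leave 1193/20 ≈ 60 to 1193/30 ≈ 40 patients in each group per parameter. Section 9.1 marks the target as still to be confirmed and dependent on uptake; at half that recruitment (an assumption) the figures are about 30 to 20, so the list should then be kept shorter.

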#### Study size

A sample size of 1193 patients in each cohort (total 2386) is desirable for this study.

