Study start is defined as the date that the first patient is recruited into the study (18th September 2015), and continue for a maximum of 36 months, or until the target sample size (1193 tbc) for both cohorts has been achieved (whichever is the soonest). The final cohort sizes, period of observation and the duration of the SCEM study will be dependent on the level of prescribing of rivaroxaban in combination with standard oral antiplatelet therapy by specialist HCPs in England and Wales. Data collected during later calendar time periods can be compared with earlier periods to identify any trends that may emerge. Slow uptake may impact on the ability to meet the study objectives; in this instance, further discussions with the regulatory authorities regarding study feasibility will be needed.

Patients will be observed from the date antiplatelet therapy was prescribed as part of the acute management of the ACS in both the rivaroxaban group and the contextual Version 7 Date: 30/08/2017

cohort for 13 weeks in order to allow for detection of outcomes associated with treatment initiation (this will allow for a delay between antiplatelet therapy administration as part of the acute treatment for the ACS, and the subsequent start of rivaroxaban to ensure 12 complete weeks of observation time for analysis). The index date for analysis for both groups will be defined dependent on the prescribing patterns observed in real life use. Since patient care is likely to be shared between secondary and primary care for most patients during the observation period, the patient's GP will be contacted at least 13 weeks after antiplatelet therapy start date to complete an abridged questionnaire to collect any information on outcomes of interest that they are aware of during the observation period to minimise under-reporting on selected outcomes. For the main statistical analysis, events will be censored at 12 weeks post index date, should they be reported after this time period. However, events of interest will be included and detailed in study reports even if they occurred after the 12 week time period. Where additional outcomes are identified that have not be reported by the initiating prescriber, these will be followed-up with the GP to ascertain further information.

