#### 9.2.2 Selection of patients

The accessible study population will be that portion of the target population of interest to whom participating HCPs have access. The identification of the study population, will be through (non-probability) systematic sampling whereby all consecutively identified eligible new rivaroxaban user patients (within the context of ACS) treated by any specialist HCP (after the pharmacotherapeutic treatment decision has been made) and who provide consent (see section 10.3) will be enrolled until the desired sample size is reached. A corresponding procedure will be used for the contextual cohort. This method will be used because a probability sampling framework is not feasible and because participation within the study is not required as a condition of receiving treatment. This approach is intended to reduce conscious or unconscious selection bias on the part of the prescriber as to whom to enrol in the study, especially with regard to prognostic factors that may be related to prognosis.

New users of rivaroxaban will be comprised of rivaroxaban patients, who may or may not be naïve to anticoagulant treatment, with no use of oral anticoagulants including rivaroxaban prior to 6 months of index date and who are newly initiated by specialist HCPs after the ACS event. In the UK, when stabilised many patients may then have medicines management transferred to the GP in primary care. Thus, the GP may take on the primary role of monitoring treatment, providing prescriptions and altering the dose when necessary, with the option of referral to secondary care if and when required. Alternatively, the patient may be primarily managed within the secondary care hospital setting alone.

<sup>1 As relevant to the date that the specialist HCP registers to participate in the study Version 7 Date: 30/08/2017

By enrolling new rivaroxaban users (an inception or incidence cohort), this study avoids the introduction of a number of biases associated with existing users (including incidence/prevalence bias, survivorship bias, and follow-up bias). Furthermore, data will be available for the contextual comparator group which will have been collected prospectively during the same calendar period, for similar indications using the same data collection methods, and all subject to the same protocol.

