A cross sectional random sample of investigative sites will be surveyed to explore the representativeness of the study population. Using medicines management audit information the demographic characteristics of patients treated for ACS will be examined and compared to those enrolled within this study.

Cohort recruitment will be examined regularly to monitor the number of evaluable patients included, so as to ensure that the desired ratio of 1:1 for the two exposure groups is achieved in the final overall study cohort for analysis.

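### The HCP and trust variances in the 9.7.2.2 prescribing model cannot be separated from site differences in recruitment, so its between-trust conclusion is not secured

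*Protocol*

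**What the plan says.** Protocol section 9.7.2.2 states that "the probability of prescribing rivaroxaban will be analysed using multilevel logistic regression analysis of pooled study data", with patients nested in HCP clinics and clinics in trusts. A base model gives the crude HCP and trust variances. Model 1 adds patient characteristics, model 2 HCP factors and model 3 trust factors. The section concludes, without qualification, that this will locate where prescribing varies and "identify whether there are significant differences in treatment decisions between trusts after taking into account individual differences".

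The sampling is described elsewhere:

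- Abstract, Study size: "A sample size of 1193 patients in each cohort (total 2386) is desirable for this study".
- Section 9.1: recruitment runs for at most 36 months, "or until the target sample size (1193 tbc) for both cohorts has been achieved (whichever is the soonest").
- Section 9.2.2: consecutively identified eligible rivaroxaban patients "and who provide consent (see section 10.3) will be enrolled until the desired sample size is reached", with a matching procedure for the contextual cohort.
- Section 9.2.2: accrual is watched "so as to ensure that the desired ratio of 1:1 for the two exposure groups is achieved in the final overall study cohort for analysis".
- Section 9.2.2: a random sample of sites is surveyed, and audit information is used to compare demographic characteristics of ACS patients with those enrolled.

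Section 9.9 adds that equal numbers on other treatments are collected in order to study selection bias.

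**The concern.** The outcome of the model is the variable that defines the two cohorts, and the cohorts are recruited to equal size. The pooled rivaroxaban share therefore approaches 50% by design, whatever share of ACS patients really receives the drug. How far one trust's share in the data departs from another's depends on two things: how often its clinicians choose rivaroxaban, and how completely that site recruits each kind of patient. The model has one variance per level and cannot tell these apart.

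At stake is a drug-utilisation conclusion under secondary objective 1. Differences in recruitment could be reported as differences in treatment decisions between trusts, or real differences in decisions could be hidden.

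**Working it through.** **1. The plan's own figure.** Inputs from section 9.5: incidence p = 0.005, precision d = 0.004, 95% confidence. n = z²p(1−p)/d² = 3.8415 × 0.004975 / 0.000016 = 1194.5. With a finite-population correction for an assumed population of 1,000,000 the result is 1193.0, which is the stated 1193. The target is sound on its own terms. Meeting it in both cohorts gives a pooled rivaroxaban share of 1193/2386 = 50%.

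**2. What sampling on the outcome does.** In one trust let the true rivaroxaban probability be π, and let fR and fC be the fractions of eligible rivaroxaban and comparator patients who are enrolled. Then

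logit(observed) = logit(π) + log(fR/fC),

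and across trusts

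Var(observed) = Var(true) + Var(log fR/fC) + 2 Cov(true, log fR/fC).

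- Ratio the same in every trust: the last two terms are 0. Only the intercept moves.
- Ratio varying independently of prescribing: its variance is added in full.
- 1:1 inside every trust: log(fR/fC) = −logit(π), so the sum is V + V − 2V = 0.

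As an example of the last case, true shares of 5% and 20% have odds 0.0526 and 0.25, an odds ratio of 4.75. If both trusts enrolled 1:1 locally, the observed odds ratio would be 1.

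**3. Does the protocol secure a common ratio?** Consecutive enrolment of both groups at every site would bring the ratio close to the ratio of consent rates. But consecutive enrolment reproduces the natural treatment mix, and that is 1:1 only if about half of eligible patients receive rivaroxaban. Sections 9.1 and 9.9 allow for slow uptake. In that case comparator enrolment has to be restrained, and no rule says how this is spread over sites. Identification also starts when each HCP registers (footnote to 9.2.2), consent is required, and section 9.9 accepts that awareness of payment may bias recruitment.

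**4. Is the ratio recorded?** No count of eligible ACS patients by treatment and site is planned. Section 9.3.1 speaks of baseline data on eligible patients who are invited, which might give consent rates, but section 9.4.1 restricts this to consented patients, and neither counts those not invited. The audit in 9.2.2 compares demographic characteristics in a sample of sites, not treatment shares.

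**5. Size.** Simulation with a two-level random-intercept logistic model fitted by maximum likelihood. Assumptions that are not in the documents: 60 trusts, 5% true share, all rivaroxaban patients enrolled, no HCP level. Entries are the median fitted trust SD (log-odds) over 60 repetitions.

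| Recruitment | True SD 0 | True SD 0.5 | True SD 1.0 |
|---|---|---|---|
| All patients | 0.00 | 0.50 | 0.95 |
| 1:1 overall, common comparator fraction | 0.00 | 0.50 | 0.99 |
| 1:1 overall, comparator fraction log SD 0.5 | 0.51 | 0.71 | 1.10 |
| 1:1 overall, comparator fraction log SD 1.0 | 0.99 | 1.10 | 1.45 |
| Same number of comparators per trust | 0.43 | 0.65 | 1.01 |
| 1:1 inside every trust | 0.00 | 0.00 | 0.00 |

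The formula in step 2 agrees: √(0.5² + 0.5²) = 0.71 and √(1.0² + 1.0²) = 1.41, against 0.71 and 1.45 fitted. Results with 30 trusts are similar.

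**The case against.** The strongest reply is that the 1:1 ratio is set for the study as a whole and for no single HCP or trust. An overall ratio does no harm to the variances if sites sample alike: the second row of the table recovers the true SD. A reader might infer that the quota by itself makes the variances a measure of recruitment and not of prescribing. The documents do not support that. Nor do they state that sites balance 1:1 locally, or that late-joining sites would meet a closed contextual cohort. Recruitment is described as concurrent and as running until both cohorts are full or time is up. The unfavourable rows in the table are possibilities that the protocol leaves open, not events that it plans.

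It can also be said that this is one descriptive analysis under a secondary objective, that the checklist in Annex 2 declares no formal hypotheses, that section 9.9 names selection bias as the chief limitation, and that section 9.7.2.2 notes that clustering can come from the sampling strategy. All of this limits the importance of the point.

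What does not stand is the unqualified conclusion about trusts. It needs a common sampling ratio, and nothing in the protocol secures or measures one. Neither 9.7.2.2 nor 9.9 connects the quota with this model. A later analysis plan could not repair this alone, because the site denominators are a matter of data collection.

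**Conclusion.** The point holds in this form: the HCP and trust variances, and the HCP-level and trust-level effects in models 2 and 3, mix prescribing with recruitment, and the two cannot be separated unless the sampling ratio of each trust is known. Absolute prescribing probabilities cannot be estimated from the pooled data in any case. Patient-level odds ratios within a trust survive, provided that enrolment there depends on treatment and calendar time and not further on the patient's characteristics.

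The size is conditional. It ranges from no distortion (common ratio), through a spurious trust SD of about 0.5 to 1.0 (log SD of comparator fractions 0.5 to 1.0, no true variation), to complete loss of a true SD of 1.0 (local 1:1 balance). The number of trusts, the 5% share and the spread of sampling fractions are all assumed. The primary bleeding incidence is estimated separately in each cohort and is not touched.

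**What to change.** 1. In 9.7.2.2, make patient-level odds ratios conditional on trust and calendar period the main result, by conditional logistic regression or trust fixed effects. If recruitment may differ between HCPs in one trust, condition on the HCP clinic where numbers allow.
2. Reword the closing statement of 9.7.2.2 so that the HCP and trust variances and models 2 and 3 describe the recruited sample, and not prescribing between trusts. Add to 9.9 that the cohorts are recruited to equal size on the outcome of this model.
3. Optionally, where a site can supply its counts of eligible ACS patients by treatment, enter log(fR/fC) for that trust as an offset. This would extend the audit in 9.2.2, which does not now collect treatment shares and covers only a sample of sites.

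Steps 1 and 2 change analysis and wording only. Step 3 needs extra data from sites. The price is that the between-trust prescribing conclusion is dropped, or limited to trusts with denominators.
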